We are postulating that by application of CGMS for 2 weeks glycemic patterns of individual patients will be identified and the education provided in this regard will change the insight of the individual towards his disease which will culminate in better longer term blood glucose control and already previous studies have shown that glucose readings from the most recent 14 days correlate strongly with 3 months of mean blood glucose, time in ranges, and hyperglycemia metrics (33,34).

Primary objective:

To study the effects of rtCGM vs isCGM on:

- Reduction in HbA1c (at the end of 3 months).

Secondary objectives:

- Reduction in glycemic variability.
- Reduction in hypoglycemic events in adults with Type-1 Diabetes.
- Reduction in Fructosamine (at the end of 2 weeks).
- Quality of life as assessed by QOLID (Nagpal etal) Questionnaire

MATERIALS AND METHODS

1. **Study design:** Open label crossover RCT with 3 arms
2. **Sample size:** Sample size of 17 is requires for a power of 80% to detect 0.5% change in HbA1c between both groups with an alpha of 0.05, Assuming 10% attrition in each group 20 patients will be recruited in all rt-CGMS and is-CGMS and 40 in SMBG arms.
3. **Subjects:** Patients attending Endocrinology OPD at PGIMER Chandigarh
4. **Study Period:** 15th June 2023 to 15th February 2024(last enrolment on 15th August 2023) and last follow up on 15th February 2024.
5. **Study Center:** PGIMER, Chandigarh
6. **Study Population:** Patients who fulfill inclusion and exclusion criteria will be recruited from OPD.

Inclusion criteria :

- Adolescents and adults ≥ 15 years with Type-1 Diabetes mellitus defined by any of the following;
 - Diabetic Ketoacidosis or ketonemia or ketonuria at diagnosis with insulin dependence for survival since diagnosis OR
 - Insulin dependence for survival since diagnosis and any one of the following autoantibody positivity: GAD-65 or IA-2
- Patients on Basal bolus regimen (**Glargine as basal and lispro/Aspart/Glulisine as bolus**);
- Duration of Diabetes > 2 years;

- Insulin dose requirement of at least 0.5U/kg
- HbA1c 8%-12%;
- Gold score<4;
- No previous experience with rt-CGMS and/or is-CGMS;
- Euthyroid status;
- If hypothyroid, then on stable dose of Levothyroxine for last 3 months with normal T4 level;
- Urine albumin creatinine ratio<300 mg/g of Creatinine;
- Those willing to give informed consent prior to enrolment.

EXCLUSION CRITERIA:

- LADA or Secondary Diabetes
- eGFR<60ml/min/1.73 m^2
- Celiac disease;

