- Hb<12g/dl for males and <11g/dl for females;
- Hypoglycemia unawareness defined by Gold score \geq 4;
- HbA1c>12%;
- DKA in previous 3 months;
- Severe Non proliferative Diabetic retinopathy/Proliferative DR/Macular edema;
- Pregnancy;
- Lactation;
- Willing to become pregnant during study;
- Requiring MRI for any existing condition;
- Any chronic illness.

METHODOLOGY

Participants meeting inclusion criteria will be randomized to rt-CGMS, is-CGMS and SMBG arms. Randomization will be done using computer generated random number list. Blocks of patients with HbA1c 8%-10% and 10%-12% will be distributed equally in all 3 groups.

Sample Size: With a 1:1:2 randomization ratio in 3 arms with sample size of 20:20:40 participants in each groups will be required.

Initial training of 2 weeks for all enrolled patients in each of 3 groups about the disease itself, ICR, ISF, carbohydrate counting and bolus dose adjustment based on these parameters will be done, for premeal boluses. **Only those patients will be enrolled who are using Lispro/Aspart/Glulisine for their diabetes control.** All adults enrolled in the rt-CGM group will be placed on rt-CGM Medtronic CGMS for 2 weeks and finger-prick blood glucose will also be monitored by glucometer (SMBG) 3 times on day 1 and then at least 2 times per day with proper record of time. All patients will use same glucometer for SMBG. Physical exercise of at least 30 mins aerobic activity will be required in all patients.

After a week a new Medtronic CGMS will be applied as per the manufacturer recommendation. Those randomized into is-CGM will be placed on Abbott Libre Flash system for 2 weeks. A 3rd group on SMBG will also be there (doing SMBG 4 times a

day- Before breakfast, Before Lunch, and Before Dinner and post meal (after any one meal on rotational basis) and **7 point profile once a week on Sunday**).

During this 2 week intervention phase all the patients will be monitored daily telephonically along with once in a week follow-up visit.

Fructosamine assay will be repeated after 2 weeks in rt-CGMS and is-CGMS groups and glycemic control compared. Thereafter the 3 groups shall use SMBG for monitoring glycemic status as in SMBG group and HbA1c will be repeated at the end of 3 months.

CGMS metrics of the 2 weeks (TBR, TIR ,TAR etc) will be compared in both groups as per ADA recommendations and those with <70% data available will be kept on a new device.

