At the end of 3 months direct cross-over of rt-CGMS group to new is-CGMS group and is-CGMS group to new rt-CGMS group will be done and again fructosamine assay shall

be done at the baseline and at the end of 2 weeks. Thereafter, all the 3 groups shall use same glucometer for SMBG till the end of 6 months where HbA1c will be estimated.

[figure not shown]
Hence, for each participant total 6 months of data will be recorded. Individuals will act as their own control thereby removing confounding factors in analysis

[figure not shown]
be done at the baseline and at the end of 2 weeks. Thereafter, all the 3 groups shall use same glucometer for SMBG till the end of 6 months where HbA1c will be estimated.

[figure not shown]
Hence, for each participant total 6 months of data will be recorded. Individuals will act as their own control thereby removing confounding factors in analysis.

[figure not shown]
All these insulins and CGM systems are a part of routine standard care in management of Type-1 Diabetes Mellitus as endorsed by American Diabetic Association in 2022.

FLOW CHART OF STUDY PROTOCOL

OUTCOME VARIABLES TO BE STUDIED

- Glycemic variability as assessed by CGMS
- Daily average insulin requirement per kg body weight
- Fructosamine assay after 2 weeks in rt-CGMS group and is-CGMS group and HbA1c in each of the 3 groups at end of 3 and 6 months respectively;
- Number of hypoglycemic events especially nocturnal and exercise related events;
- Any complications related to CGM;
- Quality of Life by QOLID (Nagpal et al) Questionnaire.

Statistical Analysis:

Statistical analysis will be performed according to the results obtained from parameters. Discrete categorical data will be represented in the form of either a number or a percentage (%), continuous data, assumed to be normally distributed, will be written as either in the form of its mean and standard deviation or in the form of its median and interquartile range, as per the requirement. The normality of quantitative data will be checked by measures of Kolmogorov-Smirnov tests of normality. ANOVA or Mann Whitney U test will be applied to compare 3 groups at a time depending upon the normality of the data. Proportions will be compared using Chi square or Fisher's exact test, depending on their applicability for 3 groups. All the statistical tests will be two-sided and will be performed at a significance level of $P < 0.05$. Analysis will be conducted using IBM SPSS STATISTICS (version 22.0)

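### The only test named for continuous outcomes compares three groups, so the primary rt-CGM versus is-CGM contrast on HbA1c and the within-person crossover data have no stated analysis

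*Combined protocol and SAP*

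**What the plan says.** The primary objective is introduced with "To study the effects of rtCGM vs isCGM on" and has one endpoint, "Reduction in HbA1c (at the end of 3 months"). The sample-size item is also framed for two groups: "to detect 0.5% change in HbA1c between both groups with an alpha of 0.05". The Methodology section promises two more two-group comparisons. For fructosamine it says "Fructosamine assay will be repeated after 2 weeks in rt-CGMS and is-CGMS groups and glycemic control compared", and the two-week CGM metrics "will be compared in both groups as per ADA recommendations". None of these statements names a test.

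The Statistical Analysis section opens by making the analysis depend on the results obtained. Its one comparison rule for continuous data is "ANOVA or Mann Whitney U test will be applied to compare 3 groups at a time", with the choice driven by normality. Chi-square and Fisher's exact test are kept for proportions, and Kolmogorov-Smirnov only checks normality. All tests are two-sided at 0.05. No t-test, pairwise contrast, multiplicity rule, paired test, mixed model, or period or sequence term appears.

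The design is a crossover in which the two CGM arms exchange devices at 3 months while SMBG continues. Its stated advantage is that "Individuals will act as their own control thereby removing confounding factors in analysis". HbA1c is listed under Outcome Variables for all three groups at both 3 and 6 months. Randomisation takes account of baseline HbA1c: "Blocks of patients with HbA1c 8%-10% and 10%-12% will be distributed equally in all 3 groups".

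**The concern.** The stated rule does not fit the stated question. A three-group omnibus test asks whether any of rt-CGM, is-CGM and SMBG differ. SMBG is half the sample (20:20:40), so a difference between CGM and SMBG can produce a significant result whether or not the two devices differ. If a pairwise follow-up is intended, the plan does not say which one, whether it depends on the omnibus result, or whether it is adjusted. Those choices would be made after the data are seen.

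The crossover has the same gap. Own-control data are its justification, but the only named method compares groups. By month 6 the CGM arms have swapped devices, so a comparison labelled by randomised arm no longer compares rt-CGM with is-CGM in the intended direction.

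**Working it through.** **The plan's own figure.** The plan states 17 for 80% power, a 0.5% difference and alpha 0.05. It gives no SD and does not say whether 17 is per arm or a number of pairs, so the figure can only be solved backwards (t distribution):
- 17 per arm, parallel: SD about 0.50.
- 17 pairs: SD of differences about 0.69.

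The figure therefore does not show which analysis was planned. For completers, 10% attrition gives 20 × 0.9 = 18 per CGM arm and 40 × 0.9 = 36 on SMBG.

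**Assumed SDs for HbA1c reduction:**
- 0.5, from the per-arm reading above.
- 0.76, from the 24-week trial of CGM versus usual care in the Review of Literature (105 and 53 participants, CI −0.8 to −0.3): 0.5/3.92 ÷ √(1/105 + 1/53) = 0.1276/0.1685 = 0.76. Rounding of the CI allows 0.61 to 0.91.
- 1.1, a baseline SD from the 60-adult rt-CGM versus is-CGM trial, reading the garbled text as 7.8 ± 1.1%. It is cross-sectional, so it is only a rough upper value for a reduction.

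**Omnibus test with identical devices.** The mean reductions relative to SMBG are −0.5, −0.5 and 0, with n = 18/18/36 and grand mean −0.25. The noncentrality is 72 × 0.25²/SD² = 4.5/SD², which is 18.0, 7.79 and 3.72. With 2 and 69 df, ANOVA rejects 97%, 69% and 37% of the time (87% to 52% over SD 0.61 to 0.91). A direct rt-is t-test rejects 5% at every SD.

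**Power for a true rt-is difference of 0.5% at month 3.** The noncentrality is 0.5/(SD × √(2/18)) = 3.00, 1.97 and 1.36. The contrasts use the pooled error on 69 df.

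| Follow-up | SD 0.5 | SD 0.76 | SD 1.1 |
|---|---|---|---|
| Unadjusted contrast | 0.841 | 0.495 | 0.270 |
| Tukey | 0.726 | 0.343 | 0.158 |
| Bonferroni (0.05/3) | 0.707 | 0.322 | 0.145 |
| Omnibus gate, SMBG midway | 0.744 | 0.368 | 0.176 |
| Omnibus gate, is 0.25% and rt 0.75% better than SMBG | 0.84 | 0.49 | 0.24 |
| Plain 18 vs 18 t-test (34 df) | 0.830 | 0.483 | 0.263 |

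The gated rows are simulated. Relative to the unadjusted contrast:
- Tukey or Bonferroni costs about 11 to 17 points.
- The gate with SMBG midway costs about 9 to 13 points.
- The gate costs 0 to 3 points once both devices beat SMBG by at least 0.25%.

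**Month 6.** Let L be the share of the period-1 device difference that persists, with a true rt benefit of 0.5%. By randomised arm, rt-first minus is-first is 0.5 × (1 − L), so rt-first looks worse by 0.50, 0.25 and 0 at L = 0, 0.5 and 1. By current device, rt looks better by the same amounts.

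**Two-period analysis of HbA1c level.** The expected estimate is 0.5 × (1 − L/2) = 0.50, 0.375 and 0.25. The assumed paired SD is 0.28/3.92 × √142 = 0.85, from the cited crossover of CGM versus conventional care, which had 26-week periods and a 17-week washout. With 36 completers the SE is 0.85/6 = 0.142, and power is 93%, 73% and 40%. These figures should not be set beside SD 0.5, because the implied within-person correlation, 1 − 0.85²/(2 × 0.5²), would be about −0.45.

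**The case against.** The two-group intent is visible. The objective, the sample size and the Methodology section all compare rt-CGM with is-CGM, and alpha is 0.05 throughout, so a sensible analyst would run an unadjusted pairwise test. The plan mentions no adjustment, so the Tukey and Bonferroni losses rest on options it does not raise. The Review of Literature concludes that CGM beats SMBG, and in that setting an omnibus gate costs almost nothing. This stands as a limit on the size of the power loss. It does not supply the missing test, because the one rule that is written compares three groups.

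A reader might take the 97%, 69% and 37% as false-positive rates. They are not: SMBG truly differs in that scenario, the plan nowhere says the omnibus p-value will be read as rt versus is, and a gated contrast would still reject only about 4–5% of the time. The point is that the result is uninformative about the devices.

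A reader might also infer that month 6 will reverse the device effect. The text speaks of new rt-CGMS and is-CGMS groups after the swap, which favours labelling by current device, and the flow chart is not available to check. Reversal needs labelling by randomised arm and less than full persistence. Month-6 HbA1c is not the primary endpoint. Sensors are also off for roughly 10 weeks before the swap (12 weeks less 2 of wear), although the Hypothesis section postulates a lasting learning effect that this interval need not remove.

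ANOVA might be meant as repeated-measures ANOVA, but the sentence compares groups and gives no within-person factor.

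**Conclusion.** The concern holds. As written, the only rule for continuous outcomes does not test the primary contrast, cannot be carried out with Mann-Whitney U on three groups, and leaves the own-control data without an analysis. This follows from the text and needs no assumed number. Mann-Whitney is by itself a naming error; the mismatch with the primary contrast is the main defect.

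The sizes do rest on assumptions. The omnibus figures of 97%, 69% and 37% assume SDs of 0.5, 0.76 and 1.1, identical devices 0.5% better than SMBG, and 18/18/36 completers. The power lost to the unstated follow-up runs from 0 to about 17 points, and no single figure is justified. Nor do the documents support three stronger inferences: that no two-group comparison is intended (several are stated), that 17 shows a parallel calculation with SD 0.5 (it may mean pairs), or that ANOVA breaks independence at month 3 (the arms are independent then).

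**What to change.** Replace the three-group sentence, before outcome data are examined, with the following:

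- **Primary test.** The rt-CGM minus is-CGM contrast in month-3 HbA1c reduction, two-sided 0.05, not gated by a three-group test. It comes from a linear model adjusted for baseline HbA1c (the blocking variable), fixed in advance with no switch driven by a normality test. A rank-based rt versus is test may be a sensitivity analysis. Contrasts with SMBG are secondary.
- **Supporting analysis.** A mixed model of HbA1c level at months 3 and 6 in the two crossover arms, with device and period as fixed effects and participant as random effect. State that sensors are off for roughly 10 weeks before the swap but no formal washout is given, and that persistence of the postulated learning effect would bias the estimate towards zero.
- **Other comparisons.** ANOVA or Kruskal-Wallis for three independent groups, and a two-sample test for two-group comparisons such as period-1 fructosamine and CGM metrics.
- **Month 6.** Label HbA1c by sequence (rt-first, is-first, SMBG), and do not read a comparison by randomised arm as a device effect.

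The cost is SAP wording and a little more analysis work, with no new data. The downside is that the carryover-free period-1 contrast has only about 26% to 83% power over the assumed SDs (plain t-test). It should be reported with the supporting estimate and its carryover caveat.

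### The analysis section never ties its tests to the named primary comparison (rt-CGM vs is-CGM, HbA1c at 3 months) and gives every other outcome and time the same P<0.05 with no hierarchy

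*Combined protocol and SAP*

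**What the plan says.** Under Primary objective, the stated aim is "To study the effects of rtCGM vs isCGM on" one item: "Reduction in HbA1c (at the end of 3 months"). Four secondary objectives follow under their own heading: glycaemic variability, hypoglycaemic events, fructosamine at 2 weeks, and quality of life by QOLID.

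The Sample size item rests on the same two-arm question: "Sample size of 17 is requires for a power of 80% to detect 0.5% change in HbA1c between both groups with an alpha of 0.05". The SMBG arm is added at double size: "With a 1:1:2 randomization ratio in 3 arms with sample size of 20:20:40 participants in each groups will be required".

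The later sections are looser. OUTCOME VARIABLES TO BE STUDIED asks for "HbA1c in each of the 3 groups at end of 3 and 6 months respectively", alongside glycaemic variability, insulin dose, fructosamine, hypoglycaemic events (with nocturnal and exercise-related events singled out), CGM complications and QOLID. Methodology adds TBR, TIR and TAR, and leaves that list open-ended. Statistical Analysis then plans ANOVA or a rank test across three groups and closes with "All the statistical tests will be two-sided and will be performed at a significance level of" P<0.05. It names no primary test, no pairwise procedure after the three-group test, no multiplicity rule and no exploratory label.

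**The concern.** A primary objective protects the conclusion only if the analysis says which test answers it. Here two links are missing.

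The first is the contrast. The primary question concerns two arms, but the planned test concerns three. A significant three-group test says that some arms differ, not which. The reference arm is SMBG, and the protocol's own literature review concludes that CGM beats SMBG, so a difference driven by SMBG alone is a realistic outcome.

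The second is the standing of everything else. Month 3 and month 6 are listed as equals, although by month 6 the device groups have swapped devices. Secondary outcomes are judged at the same threshold as the primary. With 20 patients per device arm, the primary contrast may well be inconclusive. The plan then gives no rule for how a nominal P<0.05 elsewhere should be read.

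**Working it through.** **1. The plan's own figure.** Inputs from the Sample size item: difference 0.5%, power 80%, alpha 0.05, n = 17. No SD is given. For two parallel groups, n = 2·SD²·(1.960 + 0.842)²/0.5². Solving for SD gives 0.5 × √(17/2)/2.802 = 0.52 (0.50 with a t-based calculation). So 17 per group can be neither confirmed nor refuted; it corresponds to an SD of about 0.52. With 10% attrition, 17/0.90 = 18.9, so 19; the plan recruits 20. The sizing spends the whole 0.05 on one comparison "to detect 0.5% change in HbA1c between both groups". That is sound only if one comparison is decisive.

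**2. Does a significant three-group test answer the primary question?** Suppose the two devices are equal and only SMBG is 0.5% worse. Take 90% of 20/20/40, that is 18/18/36, and the implied SD of 0.52.
- Weighted mean = (36 × 0.5)/72 = 0.25.
- Noncentrality = 72 × 0.25²/0.52² = 4.5/0.2704 = 16.6.
- Power of the F test on 2 and 69 degrees of freedom: about 95%.

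The SD is an assumption. At 0.75 the noncentrality is 4.5/0.5625 = 8.0 and the power about 70%. At 1.0 it is 4.5 and about 44%. In each case the test is often positive although the primary null is true.

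**3. All outcomes at 0.05.** With m independent tests and every null true, the expected number of false positives is 0.05·m and the chance of at least one is 1 − 0.95^m. The documents state no m, so each count is an assumption.

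| Tests counted | m | Expected | At least one |
|---|---|---|---|
| Month-3 device contrast only | 1 | 0.05 | 5% |
| Primary plus four secondaries | 5 | 0.25 | 23% |
| Each listed outcome once, HbA1c at both times | 8 | 0.40 | 34% |
| TBR, TIR, TAR, nocturnal and exercise events counted separately, each outcome once | 12 | 0.60 | 46% |
| Those 12, each in both periods | 24 | 1.20 | 71% |

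Positive correlation leaves the expected number unchanged but lowers the last column. At pairwise correlation 0.3 to 0.7, eight tests give 30% to 19%, and 24 tests give 60% to 31%.

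**4. HbA1c alone.** Suppose all three arm pairs are tested at 0.05, with no adjustment and no requirement that the three-group test be significant first. Simulation under the null gives about 12% for at least one false positive at month 3. Over months 3 and 6 it gives about 20-21% (18/18/36, within-patient correlation 0.5 to 0.7; separate simulation runs ranged from 19% to 22%). If pairwise tests are made only after a significant three-group test, the figure is about 5% at one time. Applying that gate separately at each time leaves about 8-9% over both, so gating alone does not settle which time is decisive.

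**The case against.** The strongest reply is that the protocol already has a confirmatory test. It names one contrast, one endpoint and one time, separates the secondaries by heading, and sizes the trial on that contrast. A single primary test at 0.05 needs no adjustment. This stands. A reader might infer from the blanket 0.05 rule that nothing is set apart as confirmatory, and the Primary objective contradicts that. What it does not answer is that the analysis section plans a different test and leaves the time unmarked.

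A reader might also infer that more than one false positive is to be expected. That needs more than 20 tests (20 × 0.05 = 1.00) with every null true. The documents give no count, and separate tests in each period are stated for few outcomes. The remark that individuals act as their own control points instead to one within-patient contrast per outcome. The all-null premise also sits badly with the cited trials, in which rt-CGM improved time in range and time in hypoglycaemia.

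Nor do the documents support reading any significant result as a device benefit. Two-sided errors split by direction, so only about half would favour a given device. The hypothesis concerns glycaemic control and HbA1c, which insulin dose, CGM complications or quality of life cannot establish.

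Finally, the 12% and 20-21% depend on ungated pairwise tests, which the plan does not specify. It does not exclude them either, since it is silent on what follows the three-group test.

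**Conclusion.** The point holds as a gap between sections. The primary comparison is named and sized, but the analysis does not test it specifically, does not mark month 3 as decisive, and gives every other outcome the same threshold with no order or label.

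The firmest part is the mismatch of contrast, which needs no count of tests: with the two devices equal and SMBG 0.5% worse, the three-group test is positive about 95% of the time at an SD of 0.52, falling to about 44% at an SD of 1.0. The false-positive figures are conditional. The 23% and 34% assume independent tests, all nulls true, and five or eight tests; correlation lowers them. The HbA1c figures assume three pairwise tests without adjustment or gating. Larger test counts should not be presented as a minimum or as what the plan commits to. How far a chance secondary result would shape the report cannot be calculated from the documents.

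**What to change.** Add a paragraph to Statistical Analysis to this effect:

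> The comparison of rt-CGM with is-CGM on HbA1c at month 3 is the only confirmatory test, two-sided at 0.05. All other outcomes, times and arm comparisons are secondary or exploratory and are reported as estimates with 95% confidence intervals. Where pairwise comparisons among the three arms are tested, they are Holm-adjusted or made only after a significant three-group test.

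If the investigators want significance claims for the four secondary objectives, they should state a fixed order of testing or use Holm across the four. Either is acceptable; the choice is largely one of convention. Mark month 3 as the primary time in the outcome list as well.

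This costs one paragraph, no patients and none of the primary test's alpha. The downside is that fewer outcomes can be called significant.

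### The analysis plan gives no rt-CGMS minus is-CGMS estimate or confidence interval for HbA1c, so a three-group P value cannot show whether a non-significant result excludes the 0.5% design difference

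*Combined protocol and SAP*

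**What the plan says.** Under Primary objective, the comparison is rtCGM versus isCGM and the outcome is "Reduction in HbA1c (at the end of 3 months"). The second item under Materials and Methods gives the basis for the numbers: "Sample size of 17 is requires for a power of 80% to detect 0.5% change in HbA1c between both groups". The alpha there is 0.05. Recruitment is then set: "Assuming 10% attrition in each group 20 patients will be recruited in all rt-CGMS and is-CGMS and 40 in SMBG arms". No SD is given.

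The Statistical Analysis section is the only analysis text. It lists:
- counts and percentages, means with SDs, or medians with interquartile ranges;
- a Kolmogorov-Smirnov normality check;
- ANOVA or a Mann-Whitney test applied to all three groups at once;
- chi-square or Fisher's exact tests for proportions.

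It closes with "All the statistical tests will be two-sided and will be performed at a significance level of" P < 0.05. It plans no difference between the two CGM arms, no confidence interval, no pairwise contrast and no within-patient estimate. Confidence intervals appear only in the Review of Literature.

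**The concern.** The trial asks how much better one device is than the other and names 0.5% as the difference it was built to detect, but no planned output can be set against that 0.5%. A three-group P value answers a different question. It can be significant because SMBG differs from both devices, or non-significant although the devices differ. A rank test on its own gives no effect size.

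With about 18 completers per CGM arm, non-significance has two quite different meanings: the data are tight enough to make 0.5% implausible, or they are too loose to say. An interval separates the two and a P value does not. This matters because the protocol presents itself as informing device choice where resources are limited.

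**Working it through.** **Inputs.** From the documents: two-sided alpha 0.05, power 80%, difference 0.5, n = 17, attrition 10%, recruitment 20:20:40. Completers: 20 × 0.9 = 18 per CGM arm and 40 × 0.9 = 36 on SMBG. SD: not stated.

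**The plan's own figure.** The 17 cannot be reproduced without an SD, only solved backwards. Read as 17 per arm in a two-sample comparison:
- Normal approximation: SD = 0.5 × √(17/2) / (1.960 + 0.842) = 0.52.
- t distribution: SD = 0.505.
- Attrition: 17 / 0.9 = 18.9, so 19; the plan rounds up to 20.

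The plan is thus consistent with an SD of about 0.50.

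**A second SD from the documents.** The Review of Literature quotes a parallel trial of CGM against usual care (105 versus 53) with an adjusted HbA1c difference of −0.6 (95% CI −0.8 to −0.3). Half the interval width is 0.25, so SD = 0.25 / (1.975 × √(1/105 + 1/53)) = 0.75. The quoted limits are rounded and not symmetric about the estimate; half-widths of 0.20 to 0.30 give SD 0.60 to 0.90. I take 1.0 as an assumed upper value.

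**Expected month-3 half-width**, t(0.975, 34) × SD × √(2/18) = 2.032 × SD × 0.3333:

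| SD | Half-width | P(non-significant) if true difference is 0.5 |
|---|---|---|
| 0.50 | 0.34 | 17% |
| 0.75 | 0.51 | 51% |
| 1.0 | 0.68 | 69% |

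The last column uses the noncentral t with 34 df and noncentrality 0.5 / (SD × 0.3333). The half-width equals 0.5 at SD = 0.5 / (2.032 × 0.3333) = 0.74. Below that SD an estimate of zero excludes 0.5; above it, it does not. At SD 0.50 an estimate between 0.5 − 0.34 = 0.16 and 0.34 is non-significant and still leaves 0.5 inside the interval.

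**Among non-significant results, the share whose interval still reaches 0.5% in favour of rt-CGMS** (simulation, 300,000 trials per cell, 18 per arm):

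| SD | True difference 0 | 0.25 | 0.5 |
|---|---|---|---|
| 0.50 | 15% | 56% | 86% |
| 0.75 | 51% | 81% | 95% |
| 1.0 | 70% | 88% | 96% |

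The share depends heavily on both the SD and the truth.

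**Can SMBG drive the three-group P value?** Suppose the devices are identical and SMBG is worse by d. With 18, 18 and 36 completers the overall mean lies d/2 from every group, so the noncentrality is 72 × (d/2)² / SD², tested on F(2, 69). At SD 0.75:
- d = 0.8 (assumed): 72 × 0.16 / 0.5625 = 20.5; ANOVA significant in 98% of trials.
- d = 0.6 (size in the parallel trial): 72 × 0.09 / 0.5625 = 11.5; 85%.
- d = 0.43 (size in the quoted crossover trial of CGM against conventional monitoring): 72 × 0.0462 / 0.5625 = 5.9; 56%.

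In all three cases there is no difference between the devices.

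**Crossover data.** The quoted crossover trial (142 patients, 95% CI −0.57 to −0.29) gives a within-patient SD of 0.14 × √142 / 1.977 = 0.844. With 36 completers the half-width is 2.030 × 0.844 / √36 = 0.29, assuming no carry-over or period effect.

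**The case against.** The strongest reply has four parts.

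1. **The data may be precise enough.** A reader might infer that a trial this small cannot exclude 0.5%. The documents do not support that: at the SD of about 0.50 implied by 17 per arm, the half-width is 0.34 and a near-zero estimate does exclude it. This part of the reply stands, and the point has to be conditional on the SD.

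2. **The plan does not say that non-significance means no difference.** That is correct. The hypothesis is superiority of rt-CGMS, and no rule for interpreting a null result is stated. A reader might expect such a result to be reported as no difference, or to favour a cheaper device. The first is inference. The second has no basis, since no passage says which device costs less. What remains is that nothing in the plan guards against the misreading.

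3. **Readers could work out an interval themselves.** With means, SDs and group sizes, an approximate parallel-group interval can be derived. It cannot be derived from medians and interquartile ranges, nor for the within-patient contrast. One could also read the Mann-Whitney option as pairwise, since it is a two-group test; that would supply an rt-versus-is P value but still no estimate.

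4. **The crossover is more precise.** The protocol says that individuals act as their own control, and a paired half-width near 0.29 would exclude 0.5% for a near-zero result. But the Statistical Analysis section plans no paired analysis, and the stated primary time point is 3 months, before the devices are swapped.

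**Conclusion.** The point holds as an omission that affects the primary result. The plan names the rt-CGMS versus is-CGMS contrast and a 0.5% design difference, then specifies no estimate or interval for that contrast, and its only named comparison can be significant because of SMBG alone. With 18 completers per CGM arm, the expected month-3 half-width is 0.34 to 0.68 over an assumed SD of 0.5 to 1.0. Whether a non-significant result excludes 0.5% therefore turns on an SD the documents do not give, with the crossing point at about 0.74.

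The high shares in the right-hand column of the second table apply only if the true difference is 0.5%; with no true difference at SD 0.50 the share is 15%. A reader might also infer that 0.5% should serve as a formal equivalence margin. The documents use it only for the power calculation, so the design difference can guide interpretation but should not become a pass-or-fail rule.

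The figures rest on 10% attrition, normal data with equal SDs in the arms, SDs back-solved from rounded (and in one case adjusted) published intervals, and, for the crossover figure, no carry-over or period effect.

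**What to change.** Add to Statistical Analysis:

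> The primary result is the rt-CGMS minus is-CGMS difference in month-3 HbA1c with its two-sided 95% CI (Hodges-Lehmann shift with CI if a rank test is used). The same is reported for fructosamine and CGM metrics. A non-significant result is interpreted from the CI relative to the 0.5% design difference, and is not reported as no difference when the CI includes 0.5%.

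If the crossover data are also analysed, report the within-patient difference with its 95% CI from a model with period, sequence and patient, alongside the month-3 result. State the SD behind the sample size so that the expected width can be checked.

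The cost is a little extra analysis on data already collected: no new visits, assays or patients. The one consequence to accept is that some non-significant results will have to be reported as inconclusive.
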